| Table 18 | Estimated Tissue Sample Volumes - Patients Randomized to Neoadjuvant MK-3475 | 139 |
| Table 19 | Estimated Tissue Sample Volumes - Patients Randomized to No Treatment Control Group..... | 140 |
| Table 20 | Estimated Urine Sample Volumes - Patients Randomized to Patients Randomized to Neoadjuvant MK-3475 | 140 |
| Table 21 | Estimated Urine Sample Volumes – Patients Randomized to No Treatment Control Group..... | 141 |

LIST OF FIGURES

| | |
|---|----|
| Figure 1 MK-3475-031 Trial Design..... | 14 |
| Figure 2 Relationship Between AEs and Time on Pembrolizumab (MK-3475) Therapy.... | 25 |

SUMMARY OF CHANGES

PRIMARY REASON(S) FOR THIS AMENDMENT:

| Section Number (s) | Section Title(s) | Description of Change (s) | Rationale |
|---------------------------|---|---|--|
| 5.2.1.2/5.2.1.2.1.2 | Dose Modification and toxicity Management Guidelines for Pembrolizumab/Post-Resection MK-3475 | Replaced the Dose Modification Guidelines Table. Table now includes added guidelines for dose modification in the event of myocarditis and updated guidelines for several other conditions. | To align with the most current label and safety information for pembrolizumab. |
| 5.6.2 | Supportive Care Guidelines During Post-Resection MK-3475 Treatment for this Trial | Updated the risk language and replaced the Infusion Reaction Treatment Guidelines Table. | To align with the most current safety information for pembrolizumab |

No additional changes.

1.0 TRIAL SUMMARY

| | |
|-----------------------------|--|
| Abbreviated Title | Neoadjuvant MK-3475 (pembrolizumab) RCC Study |
| Trial Phase | Phase I |
| Clinical Indication | Neoadjuvant treatment of RCC (\geq T1b) |
| Trial Type | Interventional |
| Type of control | No treatment control |
| Route of administration | Intravenous |
| Trial Blinding | Unblinded Open-label |
| Treatment Groups | Neoadjuvant MK-3475, then standard-of-care (SOC) surgical RCC resection vs. No neoadjuvant therapy, with SOC surgical RCC resection; Followed by post-resection MK-3475 for all subjects. |
| Number of trial subjects | Approximately 36 subjects will be enrolled. |
| Estimated duration of trial | The sponsor estimates that the trial will require approximately 36 months from the time the first subject signs the informed consent until the last subject's last visit. |
| Duration of Participation | After a screening phase of 1-2 weeks, each subject assigned neoadjuvant MK-3475 will receive 2 (possibly 3) Q3 week cycles of treatment followed by surgical RCC resection, while subjects not assigned to neoadjuvant treatment will proceed directly to RCC resection. Following recovery from surgery, all subjects will receive MK-3475 Q3 weeks for up to one year. After the final dose of MK-3475 each subject will be followed for 30 days for adverse event (AE) assessment. Serious adverse events (SAEs) and events of clinical interest (ECIs) will be collected for 90 days or until the initiation of new anti-cancer therapy, whichever comes first. Each subject will participate in the trial for up to approximately 18 months from the time the subject signs the Informed Consent Form (ICF) through the final Adverse Event Review. |
| Randomization Ratio | Initial randomization of 2:1 for neoadjuvant MK-3475 vs. untreated controls, with interim analysis influencing further randomization (see Sections 7.1.5.5 and 8.0). |

A list of abbreviations used in this document can be found in Section 12.6.

2.0 TRIAL DESIGN

2.1 Trial Design

This is a Phase I, randomized, no treatment controlled trial of neoadjuvant administration of MK-3475 (also known as pembrolizumab) in subjects with newly diagnosed RCC, $\geq T1b$ (>4 cm diameter), to be conducted in conformance with Good Clinical Practices. Initially, subjects will be randomized 2:1 to receive either neoadjuvant MK-3475 or serve as untreated controls. Those to receive neoadjuvant MK-3475 will undergo image-guided core needle biopsy of their tumor with collection of a minimum of three cores of tumor tissue. Tissue from this block will be used by the local pathologist to confirm the diagnosis of RCC prior to the administration of MK-3475, and remaining tissue will be used for study analyses. Blood and urine samples for biomarker analysis will also be collected at the time of core biopsy in patients randomized to receive neoadjuvant MK-3475. Two to 3 weeks after the final neoadjuvant dose of MK-3475 (administered at a dose of 200 mg IV Q3 weeks), additional blood and urine will be collected for biomarker analysis and patients will undergo SOC RCC surgical tumor resection. Control patients will proceed to surgery, without receiving neoadjuvant MK-3475, with the collection of blood and urine samples for biomarker analysis on the day of surgery. In the operating room, three or more core needle biopsy specimens of the RCC may be collected before tumor removal and prior to renal artery cross-clamping under direct vision, at the discretion of the operating surgeon and subject to local institutional review board approval. Upon surgical removal of the tumor, a minimum of 10 cm³ of non-necrotic resected tumor tissue will be collected and shipped as fresh tissue to Merck Research Laboratories for analyses. From the remaining resected tumor tissue, additional research samples will be collected for formalin fixation, snap freezing, and placement in RNAlater solution, while the remaining tumor tissue will be used by the local clinical site pathologist for routine clinical diagnostic purposes. Additional blood and urine samples for biomarker analyses will be collected from all subjects during post-operative follow up.

Following recovery from surgery, each subject may receive post-resection MK-3475. During this phase of the trial, subjects should be evaluated by SOC radiologic imaging at intervals to be selected by their treating physicians. The physician should utilize RECIST 1.1 and/or irRECIST for making clinical management decisions. AEs should be monitored throughout the trial and graded in severity according to the guidelines outlined in the NCI Common Terminology Criteria for Adverse Events (CTCAE), version 4.0.

Treatment with post-resection MK-3475 may continue until documented disease progression or recurrence, unacceptable AE(s), intercurrent illness that prevents further administration of treatment, investigator's decision to withdraw the subject, consent withdrawn by subject, start of new anti-cancer treatment, subject is lost to follow up, pregnancy of the subject, noncompliance with trial treatment or procedure requirements, completion of 17 administrations of post-resection MK-3475 (approximately 1 year of treatment), or discontinuation for administrative reasons.

After the final study visit, routine SOC clinical follow up will continue. Since the majority of recurrences (83%) after surgical resection in RCC occur within 2 years of surgery [1], the clinical outcome will be queried for each subject 1 and 2 years following surgical tumor resection.

Specific procedures to be performed during the trial, as well as their prescribed times and associated visit windows, are outlined in the Trial Flow Chart - Section 6.0. Details of each procedure are provided in Section 7.0 – Trial Procedures.

This trial will use an adaptive design based on pre-specified criteria. There will be up to three formal interim analyses. The first interim analysis will be conducted after 9 subjects have entered the trial and the immune cell infiltrates in their surgically resected RCC specimens have been assessed. The second interim analysis will be conducted after 9 additional subjects have entered the trial and the immune cell infiltrates in their surgically resected RCC specimens have been assessed. The third interim analysis may be conducted when 9 additional subjects have entered the trial and the immune cell infiltrates in their surgically resected RCC specimens have been assessed. See section 8.0 – Statistical Analysis Plan, for additional details regarding sample size determination.

The interim analyses will include re-estimations of the sample size required to maintain power in the trial. If results of the interim analyses indicate that a larger sample size is necessary, subject enrollment may be extended. Details are described in Section 8.0 – Statistical Analysis Plan. If further extension of enrollment beyond the 36 subjects proposed in this protocol is needed, a protocol amendment will be filed.

Results of the first interim analysis will be used to determine if subsequent patients recruited to participate in the study will continue to be randomized to the untreated control group that does not receive neoadjuvant MK-3475 or whether subsequent patients enrolled in the study will all receive neoadjuvant MK-3475. This determination will be made according to the pre-specified algorithm described in detail in Section 8.0 - Statistical Analysis Plan.

Results from the first interim analysis will also be used to determine if the two dose regimen for neoadjuvant MK-3475 should be increased to 3 doses, according to the pre-specified algorithm described in detail in Section 8.0 – Statistical Analysis Plan.

2.2 Trial Diagram

The trial design is depicted in [Figure 1](#).

[figure not shown]

Figure 1 MK-3475-031 Trial Design

Patients with newly diagnosed RCC ($\geq T1b$ (>4 cm diameter)) will be screened for trial participation, and after informed consent is obtained will be assigned to either undergo percutaneous image-guided core needle tumor biopsy followed by neoadjuvant MK-3475 and then SOC surgical RCC resection (top arrow) or proceed directly to SOC surgical RCC resection (bottom arrow). After recovery from surgery, all subjects may receive post-resection MK-3475.

*Initially, patients will be randomized 2:1 to neoadjuvant MK-3475 vs. untreated control, but based on prespecified interim analysis endpoints, continued randomization to the control group may be discontinued.

[†]An additional study-prescribed pretreatment core needle biopsy is not required if a diagnostic biopsy has been performed per local SOC (and within 45 days prior to the first dose of MK-3475) and sufficient tissue is available from such a specimen for the study-related analyses specified for the pretreatment core biopsy.

[‡]If RCC immune cell infiltrates are not increased by at least two-fold in more than one of the initial 6 patients receiving 2 doses of neoadjuvant MK-3475, all subsequently enrolled subjects may receive 3 doses of neoadjuvant MK-3475.

[#]Upon recovery from surgery, all subjects may receive post-resection MK-3475, 200 mg IV, Q3W, for up to one year (17 doses).

3.0 OBJECTIVE(S) & HYPOTHESIS(ES)

3.1 Primary Objective(s) & Hypothesis(es)

[figure not shown]
(1) **Objective:** To assess the safety of neoadjuvant MK-3475 therapy in patients undergoing surgical resection for the treatment of RCC

Hypothesis: Neoadjuvant MK-3475 treatment will be well tolerated in patients undergoing subsequent surgical RCC tumor resection.

[figure not shown]
(2) **Objective:** To assess the effect of neoadjuvant MK-3475 therapy on immune cell infiltration in RCC

Hypothesis: Neoadjuvant MK-3475 therapy will stimulate a 2-fold or greater increase in intratumoral lymphocytic infiltration in at least 30% of patients with RCC.

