4.2.1.3 Rationale for Sample Collection in This Trial

Discovery Sciences at Merck has a critical unmet need for clinical specimens from patients being treated with MK-3475 to help elucidate the mechanism of action of PD-1 blockade and to both identify new targets for immune modulation and guide the selection of IMRs for blockade in combination with MK-3475. This study is designed specifically to collect these critical specimens in RCC patients receiving MK-3475 in a neoadjuvant setting. Upon completion of this study, we will more fully understand the mechanism of action by which MK-3475 stimulates anti-tumor immunity, we will more clearly understand the changes in IMR expression profiles of immune cells within RCC tumors that occur during MK-3475 treatment, we will have identified numerous biomarkers potentially predictive of immune

responses stimulated by MK-3475, and we will have identified new IMR targets for Discovery Sciences to further interrogate.

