4.2.3.3 Planned Exploratory Biomarker Research

Biomarker research to identify factors important for MK-3475 treatment responses will be pursued. Tissues to be collected and assays to be performed include but are not limited to the following:

Gene expression profiling

RNA extracted from FFPE core biopsy tissue, FFPE resected RCC specimens, fresh resected RCC tissue in RNAlater solution, and whole blood will be utilized for gene profiling. Pretreatment gene expression profiles may predict which RCC tumors are infiltrated by immune cells in response to MK-3475 therapy. By comparing profiles in tumor tissues and whole blood collected before and after neoadjuvant MK-3475, changes in gene expression induced during MK-3475 treatment will be identified and will be used to more fully understand the mechanism of action of MK-3475.

Blood collection for genomic, genetic, and proteomic analysis

Blood will be collected at the time of biopsy (baseline), at the time of surgical tumor resection, and one month postoperatively. Blood collected in Paxgene tubes will also be used for DNA extraction and subsequent sequencing-based TCR utilization analysis (for correlation with intratumoral TCR utilization). Additional blood collected in Paxgene tubes will be used for RNA extraction and subsequent gene profiling for comparison to and correlation with tumor gene profiles. Whole blood samples will be analyzed by flow

cytometry to determine the phenotype of PBMC, and for subject that are HLA-A2+, pentamer staining will be performed (see below). PBMC will also be isolated from whole blood and then cryopreserved for later functional analysis.

Plasma and serum will also be collected and frozen for later analysis. Assays to be performed using plasma or serum may include but will not be limited to measurement of sPD-L1 levels using an ELISA assay recently developed at Merck, protein profiling, miRNA profiling, exosome isolation and analysis, assessment of serum antibodies, and circulating tumor DNA analysis. A recent study suggested that miRNAs 21 and 378 levels in plasma were predictive of response in patients with metastatic RCC treated with everolimus [78].

Determining the influence of tumor tissue source (FFPE vs frozen tissues) on DNA-based methods for quantitating RCC T cell infiltration

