[REDACTED]

A two-sample t-test will be used to assess the difference in the expression of pretreatment tumor PD-1 ligands between immune cell infiltration responders and non-responders among patients receiving neoadjuvant MK-3475. If normality is not deemed tenable, data transformations will be considered, or a Wilcoxon rank sum test will be used. If enrollment of controls continues after the first interim analysis, similar analyses may also be done to compare patients receiving MK-3475 relative to controls.

Tertiary PD

[REDACTED]

[REDACTED]

[REDACTED] will be compared using a Bayesian model fit that has a fixed effect for method, and a random effect for patient to account for the within-patient correlation of measurements obtained from the same patient, using flat priors and an assumption of normality. If normality is not tenable, other distributions for the number of TILs may be considered. The posterior probability that the methylation approaches are within +/-10% of the ICH approach will be quantified. A posterior probability of 50% will satisfy this tertiary hypothesis.

Exploratory PD Objectives

Many of the exploratory PD objectives will be addressed using descriptive statistics, including:

- Differences in the IMR expression profiles between RCC tumor antigen-specific CD8+ T cells and unselected TILs in patients that are HLA-A2+
- Stimulation of antigen-specific anti-tumor immune responses in patients with RCC

Other exploratory objectives will be assessed using simple measures of association of potential biomarkers with immune infiltration (i.e., Pearson's or Spearman's correlation):

- Evaluate baseline as well as changes in serum/plasma levels of proteins, miRNAs, exosomes, nucleic acids, circulating antibodies, and other biomarkers after neoadjuvant MK-3475 therapy as potential biomarkers of the immune response to therapy
- Evaluate differences in tumor tissue miRNA expression levels in response to treatment with MK-3475
- Evaluate urine exosomes as a potential biomarker of immunologic response to neoadjuvant MK-3475 treatment
- Assess changes in RCC tumor tryptophan and arginine metabolism in response to MK-3475 treatment

The above objectives may also be assessed using a two-sample t-test to look at differences between immune infiltrate responders and non-responders. If normality is not deemed tenable, data transformations will be considered, or a Wilcoxon rank sum test may be used.

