8.2.6 Interim Analysis

There will be up to 3 interim analyses done for this study. The first interim analysis will be performed after the initial 9 RCC patients, randomized 2:1 to either receive neoadjuvant MK-3475 vs. control (proceed to SOC RCC resection), have all undergone tumor resection and the assessment of tumor immune cell infiltrates has been completed. At the first interim analysis, the number of patients with an immune cell infiltration “response”, defined as a 2-fold or greater increase in the immune cell infiltrate in RCC tumor specimens compared with that in the pretreatment tumor biopsy specimens from the same patient, will be examined in the 6 patients receiving neoadjuvant MK-3475. If 4 or more of the first 6 patients receiving neoadjuvant MK-3475 respond, randomization will continue 2:1 to receive either neoadjuvant MK-3475 or control (proceed to SOC RCC resection), respectively, for the remainder of the study. If less than 4 of the first 6 patients receiving neoadjuvant MK-3475 respond, all subsequently enrolled patients may receive neoadjuvant MK-3475 with no further patients being randomized to the control group. Further, if there are 0 or 1 responders in the first 6 patients receiving neoadjuvant MK-3475, then the number of doses of MK-3475 that will be administered in patients subsequently enrolled may be increased from two to three (with the 200 mg dose and the Q3W dosing interval remaining the same). The probabilities of various outcomes after the first interim analysis are provided in [Table 12](#) below, assuming a true immune cell infiltration response rate of 5%, 30%, or 70%.

Table 12 First Interim Analysis Outcome Scenarios

Various outcomes after the first interim analysis assuming a true immune cell infiltration response rate of 5%, 30%, or 70%

| Outcome of first interim analysis | Action | Probability if true response rate = | | |
|-----------------------------------|--|-------------------------------------|-----|-----|
| | | 5% | 30% | 70% |
| 0-1 responders | Enroll all subsequent patient to MK-3475, increase from 2 to 3 doses | 97% | 42% | 1% |
| 2-3 responders | Enroll all subsequent patient to MK-3475, continue with 2 doses | 3% | 51% | 24% |
| 4-6 responders | Continue 2:1 randomization (MK-3475:Control) | < 1% | 7% | 74% |

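### The test of pretreatment tumour PD-1 ligands as predictors reads the marker in the same biopsy that forms the denominator of response, with no adjustment for baseline infiltrate

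*Combined protocol and SAP*

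**What the plan says.** Section 3.1 sets the response threshold: "Neoadjuvant MK-3475 therapy will stimulate a 2-fold or greater increase in intratumoral lymphocytic infiltration in at least 30% of patients with RCC". Section 8.2.6 defines an individual response as a "2-fold or greater increase in the immune cell infiltrate in RCC tumor specimens compared with that in the pretreatment tumor biopsy specimens" of the same patient.

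Section 8.2.4 gives the visible predictor test: "A two-sample t-test will be used to assess the difference in the expression of pretreatment tumor PD-1 ligands between immune cell infiltration responders". The comparator is the treated patients without such a response. A Wilcoxon test or a transformation is the fallback. No baseline covariate appears. For exploratory work the same section says: "Other exploratory objectives will be assessed using simple measures of association of potential biomarkers with immune infiltration", with a t-test by responder status as an option.

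Section 7.1.5.2 puts all study-prescribed cores into one cassette. Section 7.1.3.2.1.1 uses that block for infiltrate counts by IHC and DNA and for RNA profiling. Section 4.2.3.3 adds: "Pretreatment gene expression profiles may predict which RCC tumors are infiltrated by immune cells in response to MK-3475 therapy". Section 4.2.1.3 expects that by the end of the study "we will have identified numerous biomarkers potentially predictive of immune" responses.

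Section 8.2.5 allows secondary and tertiary testing only after the primary PD hypothesis is met, and then controls the false discovery rate at 10% (Benjamini-Hochberg, BH). It counts six secondary and more than eight tertiary hypotheses. It states no control for exploratory tests.

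**The concern.** If the cores happen to sample a poorly infiltrated part of the tumour, the baseline count is too low and the fold change too high. Any marker that follows local infiltrate in those cores is low as well. Low marker and response then go together by construction, even when the marker says nothing about the drug effect.

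Substantial sampling error is plausible. Table 18 puts the pretreatment cores at about 0.06 cm³, and Section 5.1.2 requires a tumour over 4 cm. A 4 cm sphere holds (4/3)π × 2³ = 33.5 cm³, so the cores are 0.06/33.5 = 0.18% of it, or less for larger tumours.

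At stake is what is carried forward. A measure of local T-cell content at baseline could be reported as a predictor of the immune response. With as few as 6 responders (Section 8.2.7), that would be hard to recognise afterwards.

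**Working it through.** **The plan's own figure.** The documents give no error rate for any predictor test. The nearest stated figure is Table 14, the probability of primary PD success, which must come first. The Beta(0.1, 0.1) prior with posterior limits of 80/70/60% needs 6/12 or 7/15, then 7/18 or 9/24, then 8/24 or 11/33 responders. An exact binomial recursion over the two allocation branches gives:

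| True rate | Recomputed (%) | Table 14 (%) |
|---|---|---|
| 30% | 13.5 / 29.6 / 44.1 | 13.0 / 29.4 / 44.0 |
| 40% | 39.1 / 68.7 / 84.8 | 39.2 / 69.3 / 84.8 |

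Section 8.2.7 states 6 of 24 for the final analysis, which gives a posterior of only 27.6%; 8 of 24 gives 62.4%. Table 14 reproduces within one point either way, so this does not affect the present point.

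**Model (assumed).** On the log2 scale, baseline in the cores is X = T + e1 and post-treatment infiltrate is Y = T + D + e2. Response is Y − X ≥ 1. SD(T) = SD(D) = 1, sampling SD s = 0.5 to 1.0, mean of D set for 30% responders. The null marker has correlation ρ with X and is unrelated to D.

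**Mechanism.** Y − X = D + e2 − e1, so Cov(X, Y − X) = −s² and

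corr(X, Y − X) = −s² / √((1 + s²)(1 + 2s²)).

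- s = 0.5: −0.25/√(1.25 × 1.5) = −0.18
- s = 0.75: −0.5625/√(1.5625 × 2.125) = −0.31
- s = 1: −1/√(2 × 3) = −0.41

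The marker inherits ρ times this, for example 0.9 × (−0.41) = −0.37. A marker that follows T alone has Cov(T, D + e2 − e1) = 0 and inherits nothing.

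**Size, unadjusted t-test at 5%, fixed n.** Each range runs from s = 0.5 to s = 1.0 (2,000 simulated trials per setting):

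| ρ | n=24 | n=33 |
|---|---|---|
| 0.4 | 6-10% | 5-10% |
| 0.7 | 8-18% | 8-23% |
| 0.9 | 10-26% | 10-35% |

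The Monte Carlo standard error at 35% is √(0.35 × 0.65/2000) = 1.1 points. Repeat runs move the s = 1 values to an overall 9-36%. At s ≥ 0.75, 88-100% of the false positives are negative in sign. Using continuous log fold change does not help: its Pearson test rejects in up to 57%.

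**Checks on the cause.** Adjusting for log baseline returns the rate to about 4-6%. Reading the marker in a core separate from the denominator gives 4.7-5.2%. A marker that tracks true tumour infiltrate gives 4.7-5.1% in the unadjusted test.

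**With the plan's controls** (adaptive n, s = 1, ρ = 0.9, BH family of 6 or 14, other hypotheses taken as null and independent):

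- 30% response rate: primary success in 44% of trials. Given success, the t-test rejects in 29%, or 17.5% (family of 6) to 10.5% (family of 14) after BH. As a share of all trials: 0.44 × 29% ≈ 13% before BH, and 7.6% or 4.6% after it.
- 40% response rate: 26% given success before BH. As a share of all trials: 22% before BH, and 12.5% or 7.6% after it.

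**The case against.** The strongest reply is that the ligand test appears under the secondary analyses, so it runs only after primary success and under BH at 10%. That stands, and it lowers the share of affected trials substantially. It does not remove the problem. Predictors are interpreted only after success, where the rate at the harsh setting is still 10-18%. BH also presumes valid p-values.

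Second, every variance and correlation is assumed. With s = 0.25 the rate is about 5-6%. That stands too, and it is why a range is given.

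Third, parts of the secondary and tertiary text are redacted, and no visible text gives the test for pretreatment gene expression. A reader might infer that it faces the same t-test; the documents do not show that.

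Fourth, the remedy is imperfect. Adjustment leaves an error for a null marker that tracks only the cores' local deviation, because X measures that deviation only partly. Requiring both tests then still passes it in 4-45% of trials. Requiring both also keeps the weaker test as a veto. For a real predictor that tracks infiltrate (drug-effect coefficient 0.7, ρ = 0.7, n=33, s = 1), power is 47% for the adjusted test, 8% for the planned test and 6.5% for both. The adjusted test alone is not a safe substitute, however: for a null marker that tracks true tumour infiltrate it rejects in 6-56% of trials.

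**Conclusion.** The point holds for tumour-core markers that share the cores' sampling error. The planned comparison can then produce a spurious inverse predictor, and no visible text guards against it. Under the assumed model the raw rate is about 5-10% with sampling SD half the between-tumour SD, and 9-36% with the two equal. For the secondary ligand test at a 30% response rate and the harshest of these settings, the plan's controls bring it to about 10-18% given primary success, or 5-8% of all trials.

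A reader might infer that a false predictor would be declared in a third of trials. The documents do not support that. The figure needs s = 1, ρ = 0.9 and n=33, and it ignores Section 8.2.5. Nor is it a ceiling: a wider grid of assumptions runs from about 5% to 78%. A reader might also infer that every correlate of baseline infiltrate is affected. Markers of true whole-tumour infiltrate are not, and blood and urine markers do not share the cores.

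The trial's primary objectives are safety and the effect on infiltration, and predictors are described only as potential. This calls for a modest improvement to the analysis, and the design can stand.

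**What to change.** In Section 8.2.4, for tumour-core markers only:

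1. Keep the planned comparison of responders with non-responders.
2. Add a regression of log post-treatment infiltrate on the pretreatment marker, adjusted for log baseline infiltrate.
3. Report both, and describe a marker as predictive only if they agree in direction and significance. Enter the larger of the two p-values into the BH family.
4. State that this reduces the artefact without removing it, since a marker that tracks only local core deviation can still pass.

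The cost is SAP wording and one regression per tumour marker, using baseline infiltrate that is already measured. No new tissue or patients are needed. The rule's false-positive rate was below that of the planned test in every setting simulated. It is 3% or less for null markers that follow either the cores' infiltrate or the true tumour infiltrate. The loss of power against the planned test was about 0-7 points.
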